5.0 Procedures Involved

5.1 Study Design:

This is a triple-blind, randomized placebo-controlled clinical trial (with blinded subjects, experimenters and statisticians) with healthy controls (cohort 1) and schizophrenia patients (cohort 2). 90 HCs, after signing consent and determining eligibility will be enrolled and randomized to receive either (i) Active 2mA right (AF4

PROTOCOL TITLE: Increased thalamocortical connectivity in tDCS-potentiated generalization of cognitive training

VERSION DATE: January 26, 2023

anode-AF3 cathode) or (ii) Active 2 mA left (AF3 anode-AF4 cathode), or (iii) Sham 0 mA tDCS during concurrent WM focused training for a total of 12 weeks. 90 SZ patients, after signing consent and determining eligibility will be enrolled and randomized to receive either (i) Active 2 mA left (AF3 anode-AF4 cathode), or (ii) Sham 0 mA tDCS during concurrent WM focused training for a total of 12 weeks. For the active stimulation, current will ramp-up for 30 seconds, remain at 2mA for 20 min and then ramp-down for 30 seconds at the end of the stimulation session. For sham stimulation, the electrodes will be placed at the same positions as for active stimulation (AF3 and AF4), but current will be turned off immediately after the initial 30 second ramp-up period. Thus, participants will feel the initial itching sensation associated with tDCS but will receive no active current for the rest of the stimulation period. This method of sham stimulation has been shown to be reliable(Gandiga, Hummel, & Cohen, 2006). To test the effects of dosage, we have scheduled a midtest and MRI scan after 6 weeks of training (approximately 15 sessions), and a posttest and scan at the completion of the protocol after 12 weeks (approximately 30 sessions). The assessment battery will be completed again at follow-up 12 weeks after the final training session.

5.2 Study Procedures:

Pre-Screening for Cohort 1 (healthy controls): Study staff or weblinks will direct interested individuals to a HIPAA compliant online portal with a thorough description of the requirements of the study. At this time, interested individuals will answer relevant screening questions, including tDCS or MRI contraindications. Volunteers will also complete items from a neuropsychological vocabulary test to estimate crystalized IQ. If the HC volunteer fulfills inclusion and exclusion criteria, they will be invited to participate and scheduled for the pretest assessment.

Pre-Screening for Cohort 2: Through a voice call or in-person meeting with study staff, or via the HIPAA-compliant online portal process described above for Cohort 1, interested individuals will be provided with a thorough description of the requirements of the study. Interested SZ volunteers will be asked screening questions about demographics, likely diagnosis, MRI eligibility and cognitive ability. Volunteers will also complete items from a neuropsychological vocabulary test to estimate crystalized IQ. Research staff will then inquire about the participant's transportation needs and offer assistance as needed to attend any in-person study appointments. If the SZ volunteer fulfills inclusion and exclusion criteria they will be invited to participate and scheduled for a pretest assessment.

Screening/Baseline Visit for Cohorts 1 and 2:

After the initial consent form has been signed, all participants will undergo the following assessments:

- The MINI – to rule out current Serious and Persistent Mental Illness (SPMI) and addictive disorders for Cohort 1, and to confirm diagnosis and rule out addictive disorders for Cohort 2.

Prior to randomization, eligible participants in both cohorts will be characterized at baseline and tracked across the study (see schedule of events tables) using cognitive tasks, clinical assessments, and neuroimaging. These include the following*:

- MATRICS Consensus Cognitive Battery Subtests (including Symbol-Coding, Category Fluency, Trailing Making Test, Spatial Span; Letter-Number Span; Hopkins Verbal Learning Test) (Cohort 1 and 2)
- UCSD-Performance Based Skills Assessment – Brief (UPSA-B) (Cohort 2 only)
- Brief Psychiatric Rating Scale (BPRS) (Cohort 2 only)
- Brief Negative Symptom Scale (BNSS) (Cohort 2 only)

* In the case that study assessment visits are conducted remotely, some of these measures (e.g. Spatial Span) will not be collected.

PROTOCOL TITLE: Increased thalamocortical connectivity in tDCS-potentiated generalization of cognitive training

VERSION DATE: January 26, 2023

Assessment activities may be audio/video-recorded. These data will be reviewed by the study team in order to achieve reliability and consistency between different interviewers and to arrive at consensus ratings for assessment scores. Assessment audio/video data will be stored on a secured UMN Box server and will only be accessible by the study team. Participants will have the choice to opt out of assessment audio/video recording in the consent form.

In addition, all participants will provide a urine or saliva sample in order to complete a drug screen. Results will be recorded.

HC participants will be randomly assigned to one of the 3 groups: (i) Active 2mA right (AF4 anode-AFP3 cathode) or (ii) Active 2 mA left (AF3 anode-AFP4 cathode), or (iii) Sham 0 mA tDCS during concurrent WM focused training for a total of 12 weeks. SZ participants will be randomly assigned to one of the 2 groups: (i) Active 2 mA left (AF3 anode-AFP4 cathode), or (ii) Sham 0 mA tDCS during concurrent WM focused training for a total of 12 weeks. Neither participants nor experimenters will know group assignment. TDCS software programming will allow staff selection of the three hemisphere conditions (right, left, sham) corresponding to eight random letters (six to be distributed evenly among three conditions for HCs, two to be distributed evenly among two conditions for SZs) encoded to preserve the blind. Randomization will be facilitated and the blinding code will be maintained by the study statistician.

Neuroimaging Assessments/MRI (Baseline, Week 6, Week 12):

Participants who are able to do in-person study visits will complete MRI sessions using the 32 channel head coil on a 3T Siemens Prisma scanner (Siemens Erlangen, Germany) located in the Center for Magnetic Resonance Research (CMRR) at the University of Minnesota at baseline, midway through the intervention and post-intervention, at 12 weeks. MRIs will not be completed if there is any concern for participant safety. This includes safety concerns during the COVID-19 pandemic.

If the research team suspects that a participant may have metal in their body, the participant may have the option to undergo a low-dose, partial- or whole-body Computed Tomography (CT) scan prior to the MRI in order to ensure their safety and eligibility. The CT scan will take place at the CMRR at the University of Minnesota. A CMRR Safety Officer will determine the level of risk to the subject and whether they are approved for MRI scanning. If approved for scanning by professionals, all risks will be conveyed to the participant so they can decide whether they wish to complete the procedure. Any concerns from the review committee will be conveyed to the participant at that time. If a participant chooses to undergo a CT scan and is subsequently found to be ineligible for the MRI scan, they will still be compensated accordingly for their time.

The MRI scan (3T) takes about 75 to 80 minutes. MRI involves taking pictures of the participant's brain, from which the properties of certain brain tissues can be measured. While sometimes MRI scans are done for clinical purposes, the scans the participant will receive are being done for research purposes. Since these scans are not designed for clinical or medical reading, the participant's scans will not receive a clinical or medical interpretation. For the scan, the participant will be asked to lie down quietly on a bed, and the bed will slide into the scanner. Once the participant is inside the scanner, it will start to take the pictures. During the scan, the participant will simply lie quietly in the scanner with eyes closed while the scanner takes images of the participant's brain. The MRI scan will be performed at the University of Minnesota's Center for Magnetic Resonance Research.

The MRI protocol:

PROTOCOL TITLE: Increased thalamocortical connectivity in tDCS-potentiated generalization of cognitive training

VERSION DATE: January 26, 2023

- Structural Imaging. High resolution whole brain anatomical T1 weighted (MPRAGE) and T2 weighted (SPACE) scans will be acquired using scan parameters matched to the HCP-lifespan protocol. Scan parameters are: T1: TE/TI/TR = 3.65/1100/2530 ms, flip angle = 7°, voxel size = 0.8 mm isotropic, scan time ≈ 7 min. T2: TE/TR = 564ms/3200 ms, variable flip angle, voxel size = 0.8 mm isotropic, scan time ≈ 6 min. The structural images will be processed through the Human Connectome Project (HCP) minimal preprocessing stream and are used in the data analysis for (a) image registration purposes and (b) structural volumetric measures for use as covariates in fMRI analysis.
- fMRI scanning. fMRI data will be collected using the HCP (<http://www.humanconnectome.org/>) multiband (MB) echo-planar sequence with parameters that closely match those used by the HCP-Lifespan project: echo time (TE) = 37 ms; repetition time (TR) = 800 ms; MB factor=8, flip angle = 52°; 72 oblique axial 2 mm thick slices; field of view (FOV) = 208 mm; 2 x 2 mm in-plane resolution (104 x 104 matrix size). The first 10 volumes will be discarded from data analysis to ensure that magnetization reached steady state. To avoid carryover task-related effects, rest will be collected before the other tasks (the order of which will be counterbalanced).
- Rest. Participants will keep their eyes open while they look directly at a small animated square which periodically rotates 45 degrees approximately every 60 to 180 seconds. Participants press a button whenever they perceive this change. This low-demand activity is used to objectively ensure that the participant is awake during the resting fMRI scan. The rest scan will have 900 volumes for a total scan time of 12 minutes.
- N-back Tasks. N-back tasks (Haut et al., 2010) will switch between 0-back and 2-back trials. A picture n-back will be done in scanner, and a word n-back will be performed the day of scan outside of the scanner. The word n-back includes one run, and the picture n-back includes two runs. Each run lasts approximately 6 minutes.
- DPX (Henderson et al., 2012; Poppe et al., 2016) task will be performed in several blocks. Each trial consists of a cue dot pattern followed by a probe dot pattern. One dot pattern was identified as a valid cue (“A” cue), and another as a valid probe (“X” probe). All other cues were invalid (“B” cues), and all other probes will be invalid (“Y” probes). Besides the valid “AX” target trials, 3 other possible combinations of cues and probes (“AY,” “BX,” and “BY”) made up 3 distinct non-target trial types enabling the identification of a specific deficit in a subject’s ability to maintain goal-relevant information throughout a trial. Timing will be jittered and each block of the DPX task will consist of 40 trials: 24 AX (6 0%), 6 AY (15%), 6 BX trials (15%), and 4 BY (10%). Each block will last approximately 6 minutes (Poppe et al., 2016).
- Field map Imaging. A pair of reverse phase encode spin echo EPI field map scans with the same prescription and voxel size as with the fMRI and with a total scan time ≈ 1 min. The field map images are used to correct the fMRI data for geometric distortions caused by magnetic field inhomogeneities as part of the HCP fMRI minimal preprocessing pipeline.

WM Training with tDCS (Weeks 1-12):

All participants will undergo WM training concurrent with tDCS. This training will consist of a target of 30 sessions of 45 minutes each in 12 weeks (target average density of 3 sessions/week), with a minimum of 24 sessions (and a minimum average density of 2/week). Individuals with fewer than 24 sessions will not be considered “complete”. The training protocol is described below:

TDCS Protocol

Before each training session, the impedance of the electrodes will be checked and verified to be ≤ 10 KOhm. During a training session, the impedance is measured every second and if found to be > 20 KOhm stimulation

PROTOCOL TITLE: Increased thalamocortical connectivity in tDCS-potentiated generalization of cognitive training

VERSION DATE: January 26, 2023

will be terminated for safety. The current and impedance will be recorded for every session. During the intervention, subjects will wear a headband with electrodes at AF4 and AF3 (right and left DLPFC)). Three different stimulation montages will be programmed: right, left and sham. Stimulation will consist of three periods: RampUp (30 sec), Constant (20 min), RampDown (30 sec). During the Ramp periods, 2 mA current will be delivered to both AF3 and AF4 with an ascending (RampUp) and descending ramp (RampDown) over 30 sec via two saline soaked electrode sponges (~ 25cm²; current density = 0.08 mA/cm²). In this way, all subjects experience the same sensation on both sides to blind them to condition. During the Constant period, current will be set based on the Condition: Right - 2mA AF4 anode-AF3 cathode; Left - 2mA applied to AF3 anode-AF4 cathode; Sham current turned off. We will test and adjust this new blinding approach on healthy subjects prior to beginning the formal study. To assess subject perceptions of the intervention, we will ask what treatment they believe they received each session.

WM Focused Cognitive Training Protocol.

WM focused training occurs on a computer and consists of a variety of exercises selected to i) place demands on the executive and storage functions of working memory ii) adapt to challenge the participant's current ability level, iii) provide ongoing feedback, and iv) present novel stimuli across verbal, visual and spatial modalities. Training tasks are developed in-house. Tasks for each subject are delivered from our AHC-IS server (cnc2.med.umn.edu). Responses of subjects and session audio and video are saved on our AHC-IS server for analysis of training performance and engagement. The aim of using multiple tasks that require WM functions is to engage thalamocortical connectivity in a number of different ways to promote generalization. The intervention will be provided by the experimenter in small groups of four or fewer participants (4:1 ratio of participants to experimenters) working under the supervision of Drs. [name] and [name], in consultation with Co-I [name], following a protocol developed by Drs. [name] and [name]. In this scheme, experimenters will monitor each participant's training and customize the intervention to balance challenge and engagement. In addition, each week participants will perform 4-minute versions of a word and a spatial 3-back task that will remain the same across all weeks (but differ from the assessment versions) to allow us to track training improvements using a constant difficulty level.

Participant effort will be rated by experimenters at each session using the Work Behavior Inventory (Bryson, Bell, Lysaker, & Zito, 1997). Just before the end of each training session, subjects will complete a brief questionnaire that also asks about their perceived engagement in the training that day, as well as their mood, previous night's sleep, discomfort, and their perceived experimental condition. Finally, at the end of each session, the participant will select the final task from an array of fun games, which we have found promotes agency and improves attendance.

Genetic sampling procedures (Baseline and Week 12):

At the baseline and post-test visit, all participants will be given the option to provide a saliva sample for genetic analyses. A study staff member will provide the participant with written step-by-step instructions for the collection of a saliva sample using the Oragene DISCOVER saliva self-collection kit (DNA Genotek, Ottawa, ON, Canada, Catalog number OGR-500) and ask the participant to not eat, drink, smoke or chew gum for 30 minutes before giving a saliva sample. The total amount of saliva collected is approximately 2 milliliters (about half a teaspoon) and will take approximately 5 minutes to complete.

Nucleic Acid (DNA) Extraction:

PROTOCOL TITLE: Increased thalamocortical connectivity in tDCS-potentiated generalization of cognitive training

VERSION DATE: January 26, 2023

Collected samples will be stored in the laboratory of [name] at the University of Minnesota ([name]). Saliva samples will be processed for DNA using the prepIT extraction kit following the manufacturer's standard protocol (DNA Genotek, Ottawa, ON, Canada, catalog number PT-L2P-5). Extracted DNA will be quantified by the Quant-iT™ PicoGreen™ dsDNA Assay Kit (Invitrogen, Waltham, MA USA, Catalog number P7589) using the Synergy HTX mult-mode plate reader (BioTek Instruments, Winooski, VT, USA).

Genetic analyses:

DNA extracted from saliva specimens will be standardized to a working concentration of 10-25ng/l prior to analyses. Targeted gene variants will be genotyped using TaqMan SNP Genotyping assays and the Applied Biosystems 7500 Real Time PCR system (Applied Biosystems, Foster City, CA, USA), Restriction Fragment Length Polymorphism (RFLP) performed by fragment analysis on the 3730 Genetic Analyzer (Applied Biosystems), or multiplexed genotyping assays performed on the MassARRAY System (Agena Bioscience) at the University of Minnesota Genomics Core facility (UMGC). Genome-wide scale genotyping will be performed using microarray or sequencing techniques in consultation with the University of Minnesota Genomics Core (UMGC). For methylation detection studies, DNA extracted from saliva specimens will be bisulfite-converted using the EZ DNA Methylation Kit (Zymo Research, Irvine, CA, USA). Bisulfite-modified DNA will be PCR-amplified using primers designed to cover target gene regions for CpG site DNA methylation detection, and sequenced using the Illumina MiSeq system following a standardized protocol at the University of Minnesota Genomics Core facility (UMGC). Genome-wide methylation assessments will be performed using the Infinium MethylationEPIC BeadChip Kit (Illumina) (or comparable alternative) which interrogates over 850,000 methylation sites quantitatively across the genome at single-nucleotide resolution.

Motivation Questionnaires (optional):

At the baseline, week 6, week 12, and week 24 visits, participants in both cohorts will be given the option to complete a set of several questionnaires which assess motivation: the Treatment Self-Regulation Questionnaire (TSRQ) (based on Williams, Freedman, & Deci, 1998), the Defeatist Performance Attitude scale (DPA) (based on Weissman & Beck, 1978), the Need for Cognition Scale (NFC) (Cacioppo & Petty, 1982), and the Behavioral Avoidance/Inhibition Scale (BIS/BAS) (Carver & White, 1994). Individual differences in these traits may moderate performance and engagement with the study intervention. Participants who complete these questionnaires will be compensated an additional \$10 for each visit they complete them (up to \$40 additional compensation).

Cognitive Effort Discounting Task (CEDT; Baseline, Week 6, Week 12, Week 24):

Individual differences in motivation for cognitive effort may moderate performance in the cognitive training intervention (i.e., inadequate effort could impede performance). In order to assess motivation for cognitive effort in a performance-based manner, participants will be given a numbers task, adding up the sum of two displayed numbers and answering via keypress if the sum starts with T, S, F, or E. Participants will choose between receiving \$5 (as a metric of points, not money paid out; hypothetical only except for random payout described below) for the harder version of this task or a value ranging from below \$5 and above \$0 for an easier version of this task. Harder tasks will range from 16 trials of the numbers task down to 4 trials. Easier tasks will range from 16> trials to >0 trials. Participants will be informed in the task instructions that they will be paid based on one of their choices in the task, selected at random. This amount will range between \$0-5 based on the task parameters. The task will last approximately 10 minutes.

PROTOCOL TITLE: Increased thalamocortical connectivity in tDCS-potentiated generalization of cognitive training

VERSION DATE: January 26, 2023

Assessment of Substance Use (Baseline, Week 6, Week 12, Week 24):

Alcohol, drug, and smoking behavior in both cohorts will be assessed at each timepoint using the Alcohol Use Disorder Identification Test (AUDIT; Saunders et al., 1993), Drug Use Disorders Identification Test (DUDIT; Berman et al., 2007) as well as several questions about smoking history and behaviors.

Schedule of Events for Healthy Controls

	Pre-screen	Screening/ Baseline Visit	Sessions 1- 15 Weeks 1-6 (2-3 times/ weekly)	Mid-Test Week 6	Sessions 16-30 Weeks 7- 12 (2-3 times/ weekly)	Post-test Week 12	Follow-up Week 24
Online screening questions	X						
IQ screen	X						
Randomization		X					
MATRICS Consensus Cognitive Battery Subtests		X		X		X	X
MINI ¹		X					
Suicide Risk Assessment		X		X		X	X
Drug Screen		X		X		X	X
Medication Review		X	X	X	X	X	X
Neuroimaging Assessment (MRI) ⁴		X		X		X	

¹ The MINI will be administered prior to randomization.

PROTOCOL TITLE: Increased thalamocortical connectivity in tDCS-potentiated generalization of cognitive training

VERSION DATE: January 26, 2023

WM Training with tDCS			X		X		
Genetic specimen collection (saliva) ²		X				X	
CEDT		X		X		X	X
AUDIT, DUDIT, & Smoking questionnaire		X		X		X	X
TSRQ, BIS/BAS, NFC, DPA ³³		X		X		X	X

² Participants will indicate in consent form whether they choose to opt in or out of genetic sampling

³ Optional questionnaires

⁴ MRIs may not occur if in-person visits are a safety concern

PROTOCOL TITLE: Increased thalamocortical connectivity in tDCS-potentiated generalization of cognitive training

VERSION DATE: January 26, 2023

Schedule of Events for SZ patients

	Pre-screen	Screening/ Baseline Visit	Sessions 1- 15 Weeks 1-6 (2-3 times/ weekly)	Mid- Test Week 6	Sessions 16-30 Weeks 7-12 (2-3 times/ weekly)	Post-test Week 12	Follow- up Week 24
Screening Questions (phone)	X						
IQ screen	X						
Randomization		X					
MATRICS Consensus Cognitive Battery Subtests		X		X		X	X
UPSA-B		X		X		X	X
BPRS		X		X		X	X
BNSS		X		X		X	X
MINI ⁴		X					
Suicide Risk Assessment		X		X		X	X
Psychosis history questionnaire		X					
Drug Screen		X		X		X	X
Medication Review		X	X	X	X	X	X
Neuroimaging Assessment (MRI) ⁷		X		X		X	
WM Training with tDCS			X		X		
Genetic specimen collection (saliva) ⁴⁵		X				X	
CEDT		X		X		X	X
AUDIT, DUDIT, & Smoking questionnaire		X		X		X	X
TSRQ, BIS/BAS, NFC, DPA ⁶		X		X		X	X

Visit windows: We will attempt to schedule study visits within approximately a one-week window (+/- one week) from the of the intended timeline. The time between a participant's screening/baseline visit and the start of their WM training (i.e., Session 1) may vary more flexibly, however. This timeframe is less critical than the timing of other visits, as it occurs before the participant receives the study intervention.

⁴ The MINI will be administered prior to randomization.

⁵ Participants will indicate in consent form whether they choose to opt in or out of genetic sampling

⁶ Optional questionnaires

⁷ MRIs may not occur if in-person visits are a safety concern

PROTOCOL TITLE: Increased thalamocortical connectivity in tDCS-potentiated generalization of cognitive training

VERSION DATE: January 26, 2023

5.3 Study Duration:

- An individual will be enrolled in the study for approximately 24 weeks total to provide complete data.
- We anticipate requiring 4 years to enroll all subjects needed for this trial

5.4 Individually Identifiable Health Information:

We have submitted the University's Privacy Office online application for data privacy and security review. We will print and upload the application with this protocol.

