75 completers in cohort 1 and cohort 2 will provide power of .80 to detect effects as small as $\eta^2=.03$ for key confirmatory analyses (tested at $\alpha = .05$) and $\eta^2=.05$ for other analyses (tested at $\alpha=.005$), with nearly as strong power for the analysis of the 24 week follow-up. The more conservative approach of intent-to-treat analysis ($n=90$) will also be conducted for Cohort 2, for which the study will be sensitive to $\eta^2=.027$ (tested at $\alpha = .05$) and $\eta^2=.042$ (tested at $\alpha = .005$). These effect sizes are much smaller than the group x time effect for generalization as measured by the MCCB in our pilot tDCS data ($\eta^2=.08$), suggesting the proposed study is well-powered. While power analyses for neuroimaging studies are challenging due to the interactions of voxelwise-thresholds, brain-wise error correction and spatial smoothness, the proposed studies will be well-powered to detect group x time voxel differences as small as $\eta^2=0.07$ (tested at $\alpha = .001$), and in any case the samples are twice the size of our previous, successfully replicated, neuroimaging studies of brain change following cognitive remediation. Within-group responder analyses conducted for completers ($n=25$ per cell) will have power of .80 to detect correlations $r \geq .34$, a lower magnitude than we already observed ($r=.55$).

15.3 Statistical Analysis:

See section 16.1

15.4 Data Integrity:

The investigator is responsible for ensuring the accuracy, completeness, legibility, and timeliness of the data reported. To enhance scientific rigor, avoid bias and enhance reproducibility, our triple-blind randomized design will use a stratified permuted block randomization procedure (Matts & Lachin, 1988) to roughly equate age and baseline WM performance across groups with a block size of 6. Neither participants nor experimenters will know group assignment. TDCS software programming will allow staff to randomly select one of the three hemisphere conditions (right, left, sham) corresponding to eight letters (six to be distributed evenly among three conditions for HCs, two to be distributed evenly among two conditions for SZs) encoded to preserve the blind. Randomization will be facilitated and the blinding code will be maintained by the study statistician.

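### Cohort 2 uses one blinding letter per arm, so a single confirmed unblinding can reveal every patient's arm; the staff-selection wording also needs reconciling with the blocked randomization

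*Combined protocol and SAP*

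**What the plan says.** Section 5.1 describes the trial as triple-blind. For the schizophrenia cohort, Section 5.2 states that "SZ participants will be randomly assigned to one of the 2 groups", left active or sham. On the coding it says: "TDCS software programming will allow staff selection of the three hemisphere conditions (right, left, sham) corresponding to eight random letters". The letters are divided as "six to be distributed evenly among three conditions for HCs" and "two to be distributed evenly among two conditions for SZs".

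Section 15.4 repeats this division. It also names the allocation method ("our triple-blind randomized design will use a stratified permuted block randomization procedure"), with the aim "to roughly equate age and baseline WM performance across groups with a block size of 6". The description of the software then reads: "TDCS software programming will allow staff to randomly select one of the three hemisphere conditions (right, left, sham) corresponding to eight letters".

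Both sections say that participants and experimenters will not know the assignment, and both give the running of randomization and the custody of the code to the study statistician. Section 10.1 plans 90 participants per cohort; Section 4.1 expects Cohort 2 to fall short of what was first anticipated, so 90 is an upper figure.

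**The concern.** A letter shared by a whole arm protects the blind only while nobody links it to its condition. With two letters for two arms there is no second layer: once one is known, so is the other. The weaker coding sits in the patient cohort.

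The stake is the conduct of training. Under the training protocol in Section 5.2, experimenters monitor each participant, tailor the exercises to balance challenge and engagement, and rate effort at every session on the Work Behavior Inventory. Section 15.1 allows that rating to be used as a covariate. Staff who know the arms could, without intending to, train or rate the two groups differently throughout Cohort 2.

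A second, smaller matter is that Section 15.4 gives two accounts of who determines the allocation: blocks run by the statistician, and a random selection by staff in the software.

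**Working it through.** **Inputs.** Letters: six over three conditions and two over two conditions (5.2, 15.4). Planned enrolment: 90 per cohort (10.1). Block size: 6, within strata of age and baseline working memory (15.4). The number of strata is not given.

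**1. The plan's own count.** Cohort 1: 6 / 3 = 2 letters per arm. Cohort 2: 2 / 2 = 1 letter per arm. Total: 3 × 2 + 2 × 1 = 8, which matches the eight letters stated.

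**2. What one confirmed link discloses**, with letters fixed and used equally:
- Cohort 1: 90 / 6 = 15 participants, or 15 / 90 = 17%. The other five letters are not decoded.
- Cohort 2: the known letter covers 45 patients and elimination gives the other 45, so 90 / 90 = 100%.
- With a separate code per participant: 1 of 90.

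**3. How likely one event is.** The documents give no unblinding rate, so this is a range of assumptions. If each patient independently has probability p of a confirmed unblinding, the chance of at least one in 90 is 1 − (1 − p)^90:
- p = 0.5%: 36%
- p = 1%: 60%
- p = 2%: 84%
- p = 5%: 99%

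One possible route is the delivered current. Sections 4.1 and 5.2 say it is recorded every session and do not say who may view it; during the constant period it would differ between active and sham.

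**4. Predictability of the next letter.** In a two-arm block of six, a person who sees the earlier letters and always guesses the less-used one expects 3 + (4³ / C(6,3) − 1) / 2 = 3 + (64 / 20 − 1) / 2 = 4.1 correct of 6, or 68% against 50% by chance. This holds only if staff can see and track the sequence within each stratum. Until the code is broken, it predicts a letter and not an arm. Mixing blocks of 4, 6 and 8 (an illustrative choice) with the sequence still visible moved the figure only from 68.3% to 67.9% in simulation. Visibility of the sequence matters far more than block size.

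**5. The two accounts of allocation.** Under stratified permuted blocks, a pre-generated order fixes each assignment. A random selection made by staff at the software would not produce balanced blocks. Section 5.2 describes the same step as staff selection, without the word randomly. The available text describes no lock between a participant and a code, and no check that the letter entered is the letter assigned.

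**The case against.** The strongest defence is that the plan works to prevent a confirmed link. All conditions share the same 30-second ramps at both electrodes, the statistician holds the code, and nothing says outright that staff see the letter at every session. This stands as a limit on likelihood. It does not change what follows once a link is made, and staff can hardly select a letter without seeing it.

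Several stronger readings are tempting, and the documents do not support them:
- *A guess about one patient decodes the cohort.* It does not. A wrong guess decodes nothing, and a right one is not known to be right.
- *Staff run simple randomization and can bypass the allocation.* The adjoining text in 15.4 specifies stratified blocks and gives randomization to the statistician. This is a wording conflict, not a stated procedure.
- *Offering three conditions contradicts a two-arm Cohort 2.* The parenthesis in the same sentence limits Cohort 2 to two conditions.
- *Unblinded experimenters rate symptoms.* The documents do not say who rates the BPRS and BNSS.
- *The key outcomes are directly compromised.* The key performance outcomes in 15.1 are N-back d', DPX d'-context and the MCCB composite, and SA1 concerns fMRI connectivity. Bias would have to come through how training was delivered.

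It is also fair to say that a change now may come late: the version is dated January 2023 and the amendment log starts in 2018.

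**Conclusion.** The concern holds for the coding of Cohort 2. One confirmed unblinding discloses up to 90 of 90 patients, against about 15 of 90 for one letter in Cohort 1. This assumes that session staff see the letter, that each letter keeps its meaning throughout, and that letters are used equally. The number falls with enrolment; the 100% share does not. The channels at direct risk are customised training and the effort rating.

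The staff-selection wording in 15.4 is a separate inconsistency to be reconciled; it is not evidence that concealment has failed. The 68% figure is conditional and secondary. This is a worthwhile correction to a stated scheme, at modest cost, and no finding that the blind has been broken.

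**What to change.** - For everyone still to be randomised, issue a unique device code per participant from the statistician's pre-generated stratified list.
- Configure the software to accept only that code for that participant, so that staff see neither a shared letter nor a sequence. This also removes the predictability issue; varying the block size would add almost nothing.
- Reword Sections 5.2 and 15.4 to say that staff enter the issued code, and remove the statement that staff randomly select a condition.

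The cost is software reconfiguration and a protocol amendment, with no added participants. Patients already coded gain nothing: one confirmed link would still disclose all of those who carry the two letters.
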